The Effect of Baduanjin on Shoulder Function in Maintenance Hemodialysis Patients

Affiliated Hospital of Nantong University

2021-11-30

The Effect of Baduanjin on Shoulder Function in Maintenance Hemodialysis Patients

1. Research Background

Chronic kidney disease bone mineral metabolism disorders exist in maintenance dialysis (MHD) patients, with a high incidence of bone and joint pain of 58.7%. At the same time, the motor ability of patients with chronic kidney disease decreases as the disease progresses, and MD patients gradually experience muscle atrophy, decreased upper limb motor ability, slow walking, and slow sitting and standing. Long term lack of exercise further exacerbates bone and joint lesions. Studies have shown that exercise can improve joint function, alleviate joint pain, increase muscle strength, and improve inflammation in MD patients. However, due to the lack of relevant evidence-based evidence, exercise rehabilitation has not yet been included in routine clinical care plans.

Clinical needs for rehabilitation exercise research data suitable for the national conditions of MHD patients, in order to recommend reasonable, feasible, and easily acceptable exercise methods for the Chinese people. Baduanjin is a health preservation technique in ancient China that combines breathing and physical exercise. It is a multi element intervention method that integrates physical, psychological, emotional, spiritual, and behavioral factors, with moderate exercise volume and belongs to the category of aerobic exercise. Although studies have suggested that Baduanjin has a good rehabilitation treatment effect in people with shoulder joint dysfunction, there is still a lack of application data in MHD patients. This study aims to follow evidence-based medicine methods to observe the improvement of shoulder joint function in maintenance dialysis patients using Baduanjin, providing theoretical basis and data support for the exercise rehabilitation and personalized treatment of MHD patients.

References

2. Roshanravan B, Gamboa J and Wilund K. Exercise and CKD: Skeletal Muscle Dysfunction and Practical Application of Exercise to Prevent and Treat Physical Impairments in CKD. American Journal of Kidney Diseases 2017; 837-852.

2.1 Research Purpose

Main objective: To observe the effect of Baduanjin on the shoulder joint function of maintenance dialysis patients.

Secondary objective: To observe the effect of Baduanjin on the quality of life and emotions of MHD patients.

2.2 Study Description

The aim of this study is to observe the therapeutic effect of Baduanjin on improving shoulder joints in MHD patients. A total of 60 maintenance hemodialysis patients will be included and randomized into an intervention group of 30 cases and a control group of 30 cases. The intervention group underwent a 30 minute Baduanjin exercise under the guidance of a professional doctor before the dialysis day, including a 5-minute warm-up exercise, a 20 minute Baduanjin exercise, and a 5-minute relaxation exercise. The intervention group practice Baduanjin three days a week, while the control group maintain routine treatment and daily activities. Measure the indicators of each group at baseline, months 6, 12, and 18. The evaluation of shoulder joint function is based on the shoulder Constant score (which includes three dimensions: pain, daily living activities, and active range of motion); The quality of life score is based on the SF-12 score, and the emotional score is based on the Anxiety and Depression Scale.

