2.3 Grouping Criteria

Inclusion Criteria:

- Age>18 years old, ≤ 75 years old
- Maintenance dialysis treatment for ≥ 3 months, three times a week
- The six minute walking experiment were used to screen patients for suitability for Baduanjin
- Right handedness, fistula in left hand

Exclusion Criteria:

- The vascular pathway is a tunnel catheter with a polyester sheath
- The vascular pathway is a right arteriovenous fistula
- Known infectious diseases

- Individuals with primary or secondary muscle diseases, mental abnormalities, lack of autonomous behavior ability, and lack of cooperation with clinical observation and treatment.

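### Current Baduanjin practitioners are eligible, may continue as controls, and are not recorded, so any who enrol would weaken the contrast between arms

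*Combined protocol and SAP*

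**What the plan says.** Section 2.2 has patients "randomized into an intervention group of 30 cases and a control group of 30 cases". For the active arm, "The intervention group underwent a 30 minute Baduanjin exercise under the guidance of a professional doctor", and "The intervention group practice Baduanjin three days a week". The control condition is given in one clause: "while the control group maintain routine treatment and daily activities". Measurements are at baseline and months 6, 12 and 18.

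Section 2.3 sets eligibility by age, dialysis duration and frequency, handedness and fistula side, and a walking test. The walking test is the only item connected with exercise: "The six minute walking experiment were used to screen patients for suitability for Baduanjin". The exclusions concern vascular access, infection, and "Individuals with primary or secondary muscle diseases, mental abnormalities, lack of autonomous behavior ability, and lack of cooperation with clinical observation and treatment". No item concerns current or past Baduanjin, or any other regular exercise.

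Section 2.4 lists no measure of exercise at baseline or during follow-up. Section 2.5 compares the two groups by a t-test or a nonparametric test, with no stratification or adjustment.

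On how likely existing practice is, section 1 points both ways. It says that "Baduanjin is a health preservation technique in ancient China that combines breathing and physical exercise", but it also describes these patients as declining in motor ability and lacking exercise over the long term.

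**The concern.** The treatment under test needs no prescription or device, and nothing in the plan limits access to it outside the trial. A patient who already does it passes the walking test, which assesses physical capacity and not prior exposure. If allocated to control, that patient follows the protocol by carrying on as before, up to month 18. If allocated to Baduanjin, the patient enters already trained and probably has less left to gain. In both cases the patient adds less to the difference between arms than someone new to the exercise.

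Randomisation spreads such patients evenly on average but does not restore the lost contrast. Because practice is not recorded, they could not be identified afterwards. A null result would then leave two explanations that the data could not separate: that Baduanjin does not help, or that some controls were also doing it. The main objective in 2.1 depends on telling these apart.

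**Working it through.** The plan gives no power calculation, effect size, standard deviation or practice rate, so there is no stated figure to reproduce. What follows is an illustration.

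**Inputs from the plan**
- 30 patients per arm (2.2).
- Significance level 0.05 and a t-test for normally distributed data (2.5). The plan does not say one- or two-sided; two-sided is assumed.

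**Assumed inputs**
- d, the standardised effect without practitioners: the value that gives 80% power at 30 per arm.
- p, the share of practitioners: 5% to 20%.
- k, the fraction of the contrast lost in a practitioner: 1 (worst case) or 0.5.

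**Step 1: reference effect.** For a two-sample t-test with 58 degrees of freedom, the noncentrality is d × √(30/2). Solving for 80% power gives d = 0.736. The normal approximation, (1.96 + 0.84) × √(2/30), gives 0.723.

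**Step 2: diluted effect.** With practitioners balanced by randomisation, the average contrast is d × (1 − k × p).

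**Step 3: power at 30 per arm, d = 0.736**

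| p | Expected practitioners among 30 controls | Effect, k = 1 | Power, k = 1 | Effect, k = 0.5 | Power, k = 0.5 |
|---|---|---|---|---|---|
| 0% | 0 | 0.736 | 80.0% | 0.736 | 80.0% |
| 5% | 1.5 | 0.699 | 75.9% | 0.717 | 78.0% |
| 10% | 3 | 0.662 | 71.3% | 0.699 | 75.9% |
| 15% | 4.5 | 0.625 | 66.3% | 0.680 | 73.6% |
| 20% | 6 | 0.588 | 61.1% | 0.662 | 71.3% |

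A 20% share losing half the contrast is equivalent to a 10% share losing all of it, since 0.5 × 20% = 10%.

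**Step 4: a smaller effect.** With d = 0.5, power is 48% without practitioners and 40% at p = 10%, k = 1. The plan documents no margin that would absorb such a loss.

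**The case against.** **No such patient is shown to exist.** This is the strongest objection. That Baduanjin is traditional does not show that dialysis patients do it, and the background's wish for exercise acceptable to Chinese patients is an aim, not evidence of use. The same section describes lack of exercise in this population. At 5% prevalence, 1.5 controls are expected and the worst-case loss is about 4 points of power. The objection stands as to size: the loss may be small.

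**Practitioners in the control arm do not receive the intervention.** A reader might infer that they do. The text does not support it: the intervention is a doctor-guided session with warm-up and relaxation, three days a week, and unsupervised practice is not the same. The k = 1 column is therefore a worst case.

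**The comparison is not biased.** A reader might also infer that it is. Against usual care, which is what 2.2 describes, randomisation keeps the comparison valid whatever patients already do. Bias towards no effect follows only if the question is starting Baduanjin against not doing it, and the plan does not say so. Admitting patients whatever their usual activity is a defensible pragmatic choice.

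**Some control instructions may be elsewhere.** Consent pages were removed from the text available for review, so they may contain advice to controls. That would not alter the eligibility lists or the outcome list.

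None of this answers the gap in recording. Even a pragmatic usual-care trial needs to know what usual care included.

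**Conclusion.** The point holds as a limited and conditional one. On the text, a current Baduanjin practitioner is eligible, carries on if allocated to control, and cannot be identified in the analysis. Any who enrol would reduce the contrast and make a null result hard to interpret.

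The size is unknown. Under the assumed reference effect, 80% power becomes 76% to 78% at 5% prevalence and 71% to 76% at 10%, where the lower figure in each range is the worst case and the higher assumes half the contrast is lost. Both the effect and the prevalence are assumptions, and prevalence may be low. The change is worth making because it is cheap and settles who is being compared with whom.

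**What to change.** 1. In 2.3, add an exclusion for current regular Baduanjin practice, for example at least weekly in the 3 months before randomisation, established by one question at screening.
2. In 2.4, record Baduanjin and other regular exercise in both arms at baseline and months 6, 12 and 18.
3. In 2.2, state that controls are asked not to start Baduanjin during follow-up.

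Patients who do other exercise, such as Tai Chi, need not be excluded. A weekly Tai Chi user moved to guided Baduanjin three days a week would plausibly still show a contrast, so recording is enough. If the sponsor prefers to keep current Baduanjin practitioners eligible, item 2 is the minimum, because it lets the result be interpreted.

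The cost is one exclusion line, one sentence on the control condition, one screening question, and an exercise question at visits already planned in 2.2. The downside is a few candidates lost at screening and slightly narrower generalisability.

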2.3 Grouping Criteria

Inclusion Criteria:

- Age>18 years old, ≤ 75 years old
- Maintenance dialysis treatment for ≥ 3 months, three times a week
- The six minute walking experiment were used to screen patients for suitability for Baduanjin
- Right handedness, fistula in left hand

Exclusion Criteria:

- The vascular pathway is a tunnel catheter with a polyester sheath
- The vascular pathway is a right arteriovenous fistula
- Known infectious diseases

- Individuals with primary or secondary muscle diseases, mental abnormalities, lack of autonomous behavior ability, and lack of cooperation with clinical observation and treatment.

2.4 Outcome Measures

Primary Outcome Measure:

1) Shoulder joint function score

Using the adjusted version of the CMS scoring scale, the total score is 75 points, including pain (15 points), daily living ability (ADL, 20 points), and joint range of motion (ROM, 40 points).

2) Shoulder joint internal rotation function

The patient takes a standing position and measures the distance between the fingers and vertebrae of the hemodialysis patient's fistulae and non fistulae hands, that is, the patient moves their thumb with the backhand as much as possible along the midline of the back, and uses a tape measure to measure the closest distance from the tip of their thumb to the spinous process of the 7th cervical vertebra. Relevant data is organized and recorded.

3) Muscle strength measurement

Grip strength can reflect the strength of the hand muscles, and a grip strength meter is used to measure the grip strength of the patient's hands separately. The patient takes a standing position, holds the handle with maximum force, and records the value when the number on the machine display screen no longer changes. Test three times, take the maximum value, and record the relevant results.

4) Area of biceps brachii muscle

Measure the thickness of the biceps brachii muscle in two groups of patients through skeletal muscle ultrasound examination.

Secondary Outcome Measures:

1) Changes in the Short Form-36 (SF-36) and European Quality of Life Five Dimension (EQ-5D-5L)

Changes from the Short Form-36 (SF-36) and European Quality of Life Five Dimension (EQ-5D-5L) scale at 0 months, 8 months, 12 months. The SF-12 score is used to evaluate an individual's health status and quality of life. The SF-12 score expressed as a number between 0 and 100, with higher numbers indicating better health. EQ-5D-5L evaluate quality of life from five aspects: action ability, self-care, daily activities, pain or discomfort, anxiety or depression. The score range generally ranges from less than 0 to 1, and the higher the score, the better the state; The VAS score range is 0-100, with

higher scores indicating better health status.

2) Changes in the Hospital Anxiety and Depression Scale (HADS)

Changes from HADS Index at 0 months, 8 months, 12 months. HADS consists of 14 items, of which 7 items assess depression and 7 items assess anxiety. The scores for anxiety and depression range from 0 to 21, with higher scores indicating more severe symptoms.

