2.5 Statistical analysis, confidentiality plan

In terms of statistical analysis, SPSS 23.0 statistical software is used to establish a database and perform statistical processing. Descriptive statistical analysis, qualitative indicators are described as percentages, and quantitative indicators are described as mean \pm standard deviation. The data is subjected to normality testing and corresponding testing methods are adopted based on whether it follows a normal distribution. Qualitative data comparison adopts chi square test. Quantitative data conforms to normal distribution, t-test is used for comparison between two groups, and nonparametric test is used for abnormal distribution and $P<0.05$ is considered statistically significant.

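### Grip strength and biceps thickness rank as primary under a shoulder-only main objective, and no rule says which primary decides, so either could alone be reported as a positive primary result.

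*Combined protocol and SAP*

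**What the plan says.** All references are to the combined protocol and SAP.

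- **Objectives (2.1).** The main objective is "To observe the effect of Baduanjin on the shoulder joint function of maintenance dialysis patients". The secondary objective is "To observe the effect of Baduanjin on the quality of life and emotions of MHD patients". Neither mentions muscle strength or muscle size.
- **Instrument (2.2).** "The evaluation of shoulder joint function is based on the shoulder Constant score", with pain, daily living activities and active range of motion as its dimensions.
- **Primary outcomes (2.4).** Four numbered items share the primary heading, without hierarchy:
  1. the shoulder score: "Using the adjusted version of the CMS scoring scale, the total score is 75 points";
  2. "Shoulder joint internal rotation function", measured as the distance from thumb tip to the seventh cervical vertebra;
  3. grip strength in each hand, introduced by "Grip strength can reflect the strength of the hand muscles";
  4. the biceps, headed as an area but described as a thickness: "Measure the thickness of the biceps brachii muscle in two groups of patients through skeletal muscle ultrasound examination".
- **Decision rule (2.5).** P<0.05 "is considered statistically significant". The section does not say which primary outcome, or how many of them, must meet it.

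**The concern.** A primary outcome should answer the main objective. Here the objective concerns the shoulder joint, but half of the primary list (two of four items) does not measure shoulder pain, activity or range of motion. Because the four items have equal rank and no deciding rule, the plan does not settle in advance what result would answer its own question.

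An exercise programme might raise grip strength or muscle thickness without changing the shoulder joint. In that event the report could state that a primary outcome was met, in a trial whose title and main objective are about the shoulder, although the CMS and internal rotation showed nothing. In the opposite event (CMS better, grip unchanged) the plan gives no guidance on whether the main objective has been met.

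**Working it through.** The plan gives no effect size, standard deviation or power for its 60 patients, so there is no stated figure to reproduce. The check has two parts.

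**1. Objective against outcome list**

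| Primary item in 2.4 | Matches the main objective in 2.1? | Covered by the instrument in 2.2? |
|---|---|---|
| Adjusted CMS (pain 15 + ADL 20 + ROM 40 = 75) | Yes | Yes |
| Internal rotation | Yes, headed as shoulder | Not named |
| Grip strength | No; described as hand muscles | No |
| Biceps thickness | No link stated | No |

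Grip and biceps do not fit the secondary objective either, since that covers only quality of life and emotions. As listed, they serve no stated objective.

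**2. How often a non-shoulder item could be the only positive primary**

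Inputs from the documents: 30 per arm (2.2), threshold 0.05 (2.5), four primaries (2.4).

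My assumptions: two-sided tests; one test per outcome; any one significant primary counts as positive; independent outcomes unless stated; power by the normal approximation.

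*No true effect.*
- At least one of four significant: 1 − 0.95⁴ = 18.5%.
- Grip or biceps significant: 1 − 0.95² = 9.75%.
- Neither shoulder measure significant: 0.95² = 90.25%.
- Both together: 0.0975 × 0.9025 = 8.8%, which is 0.088 / 0.185 = 47% of all false-positive primary results.
- With an equal correlation of 0.3, 0.5, 0.7 or 0.9 among the four test statistics (simulation), the 8.8% falls to 7.9%, 6.5%, 4.7% or 2.3%.

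*True effect on grip only,* standardised size d:
- Power = Φ(d × √(30/2) − 1.96).
- Chance that grip or biceps is significant and neither shoulder measure is = [1 − (1 − power) × 0.95] × 0.95².

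| d (assumed) | Power for grip | Non-shoulder item is the only positive primary |
|---|---|---|
| 0.5 | 49% | (1 − 0.509 × 0.95) × 0.9025 = 47% |
| 0.73 | 81% | (1 − 0.193 × 0.95) × 0.9025 = 74% |
| 0.8 | 87% | (1 − 0.127 × 0.95) × 0.9025 = 79% |

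*Would a multiplicity adjustment remove this?* It depends on the type.
- An equal Bonferroni split (0.05 / 4 = 0.0125 each) would not. With no true effect the chance is (1 − 0.9875²) × 0.9875² = 2.4%, and power for grip alone is still 29% at d = 0.5 and 73% at d = 0.8.
- A fixed sequence that tests the CMS first would, because testing stops if the CMS is not significant.

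*After the change.* With the CMS alone deciding, the chance that grip or biceps carries the main conclusion is zero by construction, and the type I error for the main objective is 5% if the CMS is tested once. Keeping both shoulder measures as equal primaries would leave 1 − 0.95² = 9.75% if they are independent.

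**The case against.** **A grip result would not be called a shoulder result.** Section 2.2 ties shoulder function to the Constant score, and in 2.4 only the first two items carry shoulder in their heading. This stands. A reader might infer that the plan treats grip or biceps as evidence of shoulder function, or that the trial would claim a shoulder benefit from them. No section says so, and 2.2 points the other way. What remains is narrower: 2.2 describes measurement and is not a success rule, 2.4 does not follow it, and nothing stops a grip or biceps result from being reported as a positive primary result.

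**This is only a multiplicity problem.** In part. A reader might infer that no correction across the four outcomes could help, but a fixed sequence starting with the CMS would. An unordered split would not, so the ranking has to be settled whichever adjustment is chosen.

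**The plan's own words concern grip only.** Correct. The hand-muscle description does not extend to the biceps. For the biceps the point rests on the plan's silence about any link to the shoulder.

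**Muscle belongs to the rationale.** Section 1 cites muscle atrophy, reduced upper-limb ability and gains in strength with exercise. That justifies measuring both outcomes, but not primary rank under an objective confined to the shoulder. Widening the main objective to upper-limb function and strength would also cure the mismatch, but it would change the trial's question and would still need a deciding rule.

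**Conclusion.** The point holds as a mismatch between objective and outcomes, together with a missing deciding rule. Two of the four equally ranked primaries are not shoulder measures on the plan's own account: grip by its description, and biceps because no link is given. Either could be the only positive primary result.

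The mismatch and the missing rule are read directly from 2.1, 2.2, 2.4 and 2.5 and need no assumption. The probabilities are illustrative: 2.3% to 8.8% with no true effect, depending on correlation, and about 47% to 79% with a real effect on grip alone. They rest on the assumed rule that any one primary suffices, one test per outcome, and assumed effect sizes; the second range also assumes independence. The documents do not support a forecast of how the result would in fact be worded, and none is made here. The point should be corrected, because it affects the headline conclusion and is cheap to resolve.

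**What to change.** - **In 2.4,** name the adjusted CMS as the outcome that decides the main objective, as 2.2 already implies. Make internal rotation supportive, or test it only if the CMS is significant.
- **In 2.4,** move grip and biceps to the secondary outcomes, labelled upper-limb strength and muscle size.
- **In 2.1,** add a secondary objective on upper-limb strength and muscle size. Without it, the two measures would still match no objective.
- **In 2.5,** state that the conclusion on shoulder function does not rest on grip or biceps.

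The cost is a text change in three sections. Every measurement is kept and the sample size is unaffected. The downside is that a gain in grip or biceps can no longer carry the headline claim.

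### The trial is open-label in effect, and the plan neither separates exercise delivery from outcome measurement nor masks any assessor of the primary outcomes

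*Combined protocol and SAP*

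**What the plan says.** **Design (section 2.2).** Sixty patients are "randomized into an intervention group of 30 cases and a control group of 30 cases". The exercise arm "underwent a 30 minute Baduanjin exercise under the guidance of a professional doctor before the dialysis day", "while the control group maintain routine treatment and daily activities". No sham or attention control is described.

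**Who measures (section 2.2).** The only general instruction is "Measure the indicators of each group at baseline, months 6, 12, and 18". It names no assessor.

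**Primary outcomes (section 2.4).** There are four:

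- An adjusted CMS shoulder score out of 75: pain 15, daily living 20, range of motion 40. Section 2.2 describes the range of motion as active.
- Internal rotation. The patient reaches up the back as far as possible, and the measurer "uses a tape measure to measure the closest distance from the tip of their thumb" to C7.
- Grip strength. The patient "holds the handle with maximum force, and records the value when the number on the machine display screen no longer changes"; the best of three attempts is kept.
- Biceps size: "Measure the thickness of the biceps brachii muscle in two groups of patients through skeletal muscle ultrasound examination".

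Section 2.4 does not say who takes any of these, whether that person knows the arm, how encouragement is standardised, or how ultrasound images are labelled when they are measured. Section 2.5 (statistics), section 2.6 (records and confidentiality) and section 3 (exit criteria) add no safeguard. Nothing in the available text mentions masking of anyone.

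**The concern.** Guided exercise cannot be hidden from the patient or from the doctor who guides it. In such a trial the main remaining protection against measurement bias is an assessor who does not know the arm, and the plan does not provide one.

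The primary outcomes differ in how exposed they are. Range of motion, the tape reading and the ultrasound measurement leave room for the examiner's judgement: where the movement is taken to end, where the tape is placed, and how the image is acquired and measured. Grip leaves less room, because the value comes from a display, but the examiner can still encourage one arm harder than the other.

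A shift in the readings that favours exercise looks the same in the data as a treatment effect. The two-group tests planned in section 2.5 cannot tell them apart, and the shift cannot be removed once the data are collected.

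**Working it through.** **1. Is the trial open-label?** The documents do not use the term. Section 2.2 sets doctor-guided sessions against routine treatment without a sham. Patients and the guiding doctor therefore know the allocation, and the inference is sound.

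**2. Is measurement separated or masked?** Sections 2.2 and 2.4 are the two places where a safeguard would be expected. Section 2.2 says when to measure and section 2.4 says what and how. Neither says who. The documents neither assign the measurements to the guiding doctor nor forbid it.

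**3. What could a masked assessor protect?** From the points in section 2.4:

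- Range of motion: 40/75 = 53.3% of the shoulder score. It is examiner-scored, but active, so it also depends on patient effort.
- Pain and daily living: (15 + 20)/75 = 35/75 = 46.7%. A masked assessor does not remove the patient's knowledge of the arm from these.
- Thumb-to-C7 distance: examiner reading plus patient effort.
- Grip: display reading, so mainly encouragement and patient effort.
- Biceps ultrasound: mainly operator and reader.

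**4. The plan's own figure.** The sample size of 60 cannot be reproduced, because the plan gives no effect size, SD, power or dropout. The point does not depend on it.

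**5. Scale of the possible effect.** From the documents: n = 30 per arm (section 2.2), a t-test for normally distributed data and P < 0.05 (section 2.5). Assumed: a two-sided test, since section 2.5 does not state sidedness; no true effect; and a constant measurement shift of b SD in favour of exercise. The documents give no value for b.

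- Degrees of freedom: 2 × 30 − 2 = 58; critical value t = 2.002.
- Noncentrality: b × √(n/2) = b × √15 = b × 3.873.
- Chance of a significant result: P(T > 2.002) + P(T < −2.002), with T noncentral t on 58 df.

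| Assumed shift b (SD) | Noncentrality | Significant in favour of exercise | Significant, two-sided |
|---|---|---|---|
| 0 | 0 | 2.5% | 5.0% |
| 0.1 | 0.387 | 5.7% | 6.7% |
| 0.2 | 0.775 | 11.5% | 11.9% |
| 0.3 | 1.162 | 20.7% | 20.8% |

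These are rates for one outcome. A shift of 0.1 SD inflates the error modestly, 0.2 SD more than doubles it (11.9/5.0 = 2.4) and 0.3 SD roughly quadruples it (20.8/5.0 = 4.2). For comparison, the true effect detectable with 80% power at 30 per arm is about 0.74 SD.

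**The case against.** The strongest reply is that the defect is silence and not a stated practice. The site may already use separate assessors, and the plan would read the same. That is right, and it limits the claim: a reader might infer that the guiding doctor scores the outcomes, or that every primary outcome is measured unmasked, and the documents show neither. The silence still matters, because the plan can be followed exactly with arm-aware measurement throughout.

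Second, grip is a poor example of examiner discretion, since the number comes from a machine. This stands for the reading. It does not cover encouragement, for which no script is given.

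Third, masking the assessor is only a partial remedy. Active range of motion, reach and maximal grip depend on the effort of a patient who knows the arm, and pain and daily living are 35 of the 75 points. This stands in full. Only ultrasound images measured under a code come close to masked measurement.

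Fourth, the error rates rest on an assumed shift. This also stands. A reader might infer that any small shift pushes the error rate well above 5%, but 0.1 SD gives only 6.7%.

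Finally, text after section 4.1 was not available for this review. It follows the ethics section and is unlikely to hold a masking plan, but this could not be checked.

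**Conclusion.** The concern holds as an omission. The trial is open-label in effect, and nothing in the available text masks an assessor or keeps the person delivering the exercise away from the measurements. The exposure is clearest for range of motion, the thumb-to-C7 reading and biceps ultrasound, and weaker and indirect for grip.

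The size of any bias in this trial is unknown. The inflation is material only if the shift is around 0.2 SD or more, and the calculation rests on an assumed constant shift, a two-sided t-test and no true effect. It shows scale and does not estimate this trial's error rate.

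The change should be made, because prevention is cheap and later correction is not possible. It is not grounds for saying that the results will be biased.

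**What to change.** Add to section 2.4:

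1. Biceps images are saved under a study code and measured without arm or visit labels.
2. The doctor who guides Baduanjin does not score range of motion, thumb-to-C7 distance or grip. Where an existing staff member who does not attend the sessions is available, that person takes these measurements without being told the allocation, and patients are asked not to reveal their group.
3. One fixed script is used for grip and reach instructions in both arms.

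Report the range-of-motion subscore separately and call it *assessor-masked*, not *blind*, and only if item 2 was achieved. State in the report that pain, daily living and patient effort remain open to bias.

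**Cost.** The arms, sample size and visits do not change. The additions are some scheduling, the handling of coded images and a script. The cost is low on the assumption that suitable existing staff are available; the documents give no staffing. If they are not, coded images and the script can still be adopted. Patients will occasionally reveal their group.
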